3.6 Eligibility

Inclusion criteria

- 3 - Clarified definition of macular edema for eligibility by adding specific eligibility thresholds for central subfield macular thickness for different types of OCT machines
- 4 - Removed upper limit of best corrected visual BCVA (i.e., worse than 20/32)
- 5 – Increased the number of IOP lowering medications permitted from 2 to 3 and added clarification that combination medications, i.e., Cosopt, count as 2 IOP lowering medications

Exclusion criteria

- 3 - New patient-level exclusion added: History of central serous retinopathy in either eye
- 6 – Clarification added as italicized for exclusion for oral prednisone dose ≤ 10 mg per day *at baseline* that has not been stable for at least 4 weeks (*Note if patient is off of oral prednisone at baseline (P01 visit), dose stability requirement for past 4 weeks does not apply*);
- Deleted exclusion criterion: Topical NSAID use if dose has not been stable for at least 4 weeks.

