3.5. Secondary outcomes

- Rate of IOP elevation of >21 mm Hg or \geq 10 mm Hg from baseline during the 24 weeks of follow-up
- Percent change in macular thickness as measured by OCT over the 24 weeks of follow-up
- Proportion of eyes with macular edema events over the 24 weeks of follow-up
 - \geq 20% reduction in macular thickness (or normalization of macular thickness even if there is <20% reduction)
 - "Resolution", defined as normalization of the macular thickness to within \pm 2 standard deviations of the normative mean for the OCT machine used
 - Worsening defined as a 20% increase in macular thickness from the lowest value after an injection
 - "Recurrence" defined as >20% increase in the central subfield measurement on OCT to an abnormal value in an eye that previously had resolution of ME
- Mean change in BCVA over the 24 weeks of follow-up.
Best-corrected visual acuity score will be measured at every study visit under standardized lighting conditions by certified study examiners masked to study treatment using logarithmic (ETDRS) visual acuity charts, according to the method described by Ferris, et al.⁷⁵
- Inflammation as graded using the semi quantitative scales used in the MUST Trial i.e., clinician grading of the presence and extent of anterior chamber cells, anterior vitreous cells, and vitreous haze based on previously published standard ordinal scales (0, trace, 1+, 2+, 3+, 4+)⁷⁶⁻⁷⁸ using the scales endorsed by the Standardization of Uveitis Nomenclature Working Group when applicable⁷⁹
- Safety outcomes including elevated IOP (>30 mm Hg thresholds); new onset posterior subcapsular (PSC) cataract or progression of pre-existing PSC (using the Age-Related Eye Disease Study [AREDS] scheme⁸⁰; vitreous hemorrhage; retinal tear/detachment; endophthalmitis; severe vision loss (\geq 15 Early Treatment Diabetic Retinopathy Study [ETDRS] letters) during the 24 weeks of follow-up.
- Cost-effectiveness of treatments for uveitic macular edema during the 24 weeks of follow-up will be assessed by enumerating costs of treatments and procedures for uveitis during the 24 week follow-up; participants' utilities will be measure with the EuroQol questionnaire.
- Visual function related quality of life as measured by the NEI Visual Function Questionnaire (25 item version).

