3.6. Eligibility criteria

Inclusion criteria:

Patient level inclusion criterion:

1. 18 years of age or older;

Eye level inclusion criteria - at least one eye must meet all of the following conditions

2. Non-infectious anterior, intermediate, posterior or panuveitis; either active or inactive uveitis is acceptable;
3. Macular edema (ME) defined as the presence of central subfield macular thickness greater than the normal range for the OCT machine being used ($>300\ \mu\text{m}$ for Zeiss Cirrus/Topcon 3DOCT or $>320\ \mu\text{m}$ for Heidelberg Spectralis), regardless of the presence of cysts, as assessed by study ophthalmologist;
4. Best corrected visual acuity (BCVA) 5/200 or better;
5. Baseline intraocular pressure $> 5\ \text{mm Hg}$ and $\leq 21\ \text{mm Hg}$ (current use of 3 or fewer intraocular pressure-lowering medications and/or prior glaucoma surgery are acceptable – *note that combination medications, i.e., Cosopt, count as 2 IOP lowering medications*);
6. Baseline fluorescein angiogram that is gradable for degree of leakage in the central subfield
7. Pupillary dilation sufficient to allow OCT testing.

Exclusion criteria:

Patient level exclusion criteria:

1. History of infectious endophthalmitis or infectious uveitis in either eye;
2. History of infectious scleritis of any type in either eye. (*Note: History of noninfectious scleritis that has been active in past 12 months is an eye-level exclusion –see #11 below.*)
3. History of keratitis (with the exception of keratitis due to dry eye) in either eye;
4. History of central serous retinopathy in either eye;
5. For women of childbearing potential: pregnancy, breastfeeding, or a positive pregnancy test; unwilling to practice an adequate birth control method (abstinence, combination barrier and spermicide, or hormonal) for duration of trial;
6. Use of oral acetazolamide or other systemic carbonic anhydrase inhibitor at baseline;
7. Oral prednisone dose $> 10\ \text{mg}$ per day (or of an alternative corticosteroid at a dose higher than that equipotent to prednisone $10\ \text{mg}$ per day) OR oral prednisone dose $\leq 10\ \text{mg}$ per day at baseline that has not been stable for at least 4 weeks (*note that if patient is off of oral prednisone at baseline (P01 visit), dose stability requirement for past 4 weeks does not apply*);

8. Systemic immunosuppressive drug therapy that has not been stable for at least 4 weeks;

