6.2. Statistical methods

The primary analysis will adhere to the intention to treat principle regardless of treatment deviations made either in error or per the best medical judgment of the treating ophthalmologist. Evaluation of continuous outcomes over time (such as log change in retinal thickness or best corrected visual acuity) and binary outcomes over time (such as normal/abnormal IOP) will use a repeated measures analysis with Gaussian or logit links that account for the nested correlations between observations over time and between eyes of the same patient.⁹⁰ A saturated mean model, including visit and visit by treatment interaction terms, will be used. An unstructured covariance matrix will be used to model the within-eye repeated measurements augmented by random effects to induce cross-sectional between-eye associations. Alternatives, including a first-order, auto-regressive process (an AR(1) model) along with a random intercept, will be considered if the unstructured covariance model is unstable. This structure allows for correlation to decrease with increasing time-separation down to a level set by the random intercept.

Significance for superiority hypotheses in POINT will be determined by comparing the p-value of the interaction term for the week 8 visit with 0.01667 (i.e. 0.05/3). Significance for the non-inferiority hypothesis in POINT will be assessed by comparing the upper bound of the 96.7% confidence intervals for estimate of the difference in change in log retinal thickness at 8 weeks, which is estimated by the 8-week interaction term, with the defined non-inferiority boundary of 0.15 on the log scale, which is equivalent to a 10% difference in percent reduction (40% vs 30% reduction) for the two groups.

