Evaluation of risk factors for time-to-event outcomes such as incidence of cataracts, as well as time to remission will be performed using Cox proportional hazards regression as well as parametric time-to-failure models, such as gamma models⁹¹. Implementation of these models that allows for clustering (within patients and within eyes), assessment of recurrent events, and incorporation of time-dependent covariates will be used. When the relevant follow-up time in the analysis reflects the clinical time scale (e.g. time since diagnosis of uveitis), it is necessary to incorporate the prevalent cases (longstanding diagnosis of uveitis) into the analysis. To accommodate the prevalent cases we will use the staggered entry technique⁹², which is one method of adjusting for potential survival bias. The analysis compares the event rates among patients with similar duration of disease and then combines over these comparisons. Event rates for multiple recurring events, e.g. the number of adverse events, will be modeled using Poisson regression or Negative Binomial regression⁹³, including a random effects term to account for the between eye correlation.

All analyses will be performed both unadjusted, except for the stratification variable, and adjusted for potential confounders. Effect modification due to factors such as disease location or uveitis activity, fluorescein leakage in the central subfield, systemic disease, gender and race also will be explored when appropriate. Robust standard errors will be computed using statistical program-based approaches when available and a bootstrap with the individual as the sampling unit, when a pre-programmed approach is not available.

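### On its likeliest reading, the BCVA contrast is a raw difference in change; adjusting for each eye's baseline BCVA would narrow its intervals at almost no cost

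*Combined protocol and SAP*

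**What the plan says.** - **Outcome.** Section 3.5 lists as a secondary outcome "Mean change in BCVA over the 24 weeks of follow-up". It adds that "Best-corrected visual acuity score will be measured at every study visit", and the schedule in section 3.8 shows BCVA at baseline and at weeks 4, 8, 12, 20 and 24.
- **Model.** The repeated measures paragraph of section 6.2 covers "Evaluation of continuous outcomes over time (such as log change in retinal thickness or best corrected visual acuity") and says: "A saturated mean model, including visit and visit by treatment interaction terms, will be used". For log thickness, the same section describes the difference in change at week 8 as a quantity "which is estimated by the 8-week interaction term".
- **Covariates.** Section 6.2 also says: "All analyses will be performed both unadjusted, except for the stratification variable, and adjusted for potential confounders". The confounders are not listed, and neither of the two runs is designated as the main result. Baseline BCVA is not named as a covariate anywhere.
- **Entry vision and balance.** Section 3.6 requires only "Best corrected visual acuity (BCVA) 5/200 or better". Randomisation (section 3.7) is stratified on systemic uveitis therapy alone, so balance in baseline vision is left to chance.
- **Reporting.** Section 6.2 says secondary outcomes will be read mainly from estimates and confidence intervals rather than p-values.

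**The concern.** A saturated mean gives every arm its own mean at every visit, baseline included. The arm contrast at a later visit is then the plain difference in mean change. Subtracting baseline is not the same as adjusting for it. The subtraction fixes the coefficient of baseline at one, whereas the best coefficient is the regression slope of follow-up on baseline. Unless that slope happens to equal one, the change score carries avoidable noise.

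Two things are at stake. The first is the width of the BCVA intervals for all three pairwise comparisons, which matters because the plan reads secondary outcomes from their intervals. The second is exposure to chance imbalance. If one arm starts with better vision, regression to the mean makes its gain look smaller, and a raw change contrast leaves that in the estimate.

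**Working it through.** **Inputs.** The outcome, visits and model terms are those given above. The documents supply 89 participants per arm (section 3.1) and 10% loss to follow-up (section 6.1). They give no SD, correlation, target difference or power for BCVA. So rho (correlation of baseline with follow-up BCVA) and k (follow-up SD divided by baseline SD) are assumptions, shown as ranges.

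**1. The plan's own figure.** There is none for BCVA. The nearest is the OCT superiority power in section 6.1. The difference is log(0.75) − log(0.60) = 0.2231. The standard error is 0.33 × √(2/89) = 0.0495. The ratio is 4.51, and subtracting 2.394 (two-sided 0.01667) gives 2.12, so power is 98.3% against the stated 98%. It reproduces, but it says nothing about BCVA.

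**2. What the model estimates.** With a free mean for each arm and visit, the week-t contrast is (mean at t minus mean at baseline) in one arm less the same quantity in the other. This is so whether change is the response or all six visits are.

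**3. Variance at one visit, per eye, in units of baseline variance.**

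- Raw change: 1 + k² − 2·rho·k
- Adjusted for baseline: k²(1 − rho²)
- Gap: (1 − rho·k)², which is never negative

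With k = 1 these are 2(1 − rho) and 1 − rho², so the ratio is (1 + rho)/2. At rho 0.5, for example, the values are 1.00 and 0.75, and √0.75 = 0.866, which is 13% narrower.

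| rho (k = 1) | variance ratio | interval narrower by | 89 eyes per arm act like (89/ratio) |
|---|---|---|---|
| 0.5 | 0.75 | 13% | 119 |
| 0.7 | 0.85 | 8% | 105 |
| 0.8 | 0.90 | 5% | 99 |
| 0.9 | 0.95 | 2.5% | 94 |

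**4. Unequal SDs.** If good-vision eyes cannot gain much and follow-up vision is compressed, k falls below 1. At k = 0.8 and rho 0.5, 0.7, 0.8 and 0.9 the ratio is 0.571, 0.628, 0.640 and 0.608, so intervals are 20% to 24% narrower. If follow-up vision is more spread out (k = 1.2), the ratios are 0.871, 0.966, 0.997 and 0.977, and the gain is 7% at most and close to nil at rho 0.8.

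**5. Do the other visits recover the loss?** No. Generalised least squares over all six visits with equal correlations compared arm-specific baseline means with one common baseline mean. For the week 8 contrast it gave ratios of 0.75, 0.85, 0.90 and 0.95 with complete data, and 0.758, 0.855, 0.904 and 0.952 with 10% dropout.

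**6. Chance imbalance.** With k = 1, a difference D between arms in mean baseline BCVA shifts the raw change contrast by −(1 − rho)·D. That is half of D at rho 0.5 and a tenth of D at rho 0.9.

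**Scope.** Steps 3 to 5 take one eye per patient. The ratios carry over to bilateral patients if the between-eye correlation is the same for the change and for the baseline-adjusted value, because clustering then inflates both variances equally.

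**The case against.** **The plan may already be efficient.** Section 6.2 names visit and visit by treatment but no treatment main effect. With baseline as the reference visit and only those terms fitted, all arms would share one baseline mean, and the model would have the precision of baseline adjustment. This reading is possible, but a saturated mean argues against it. What stands is that the text admits models of different precision and should say which is meant.

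**The adjusted run may cover it.** Baseline BCVA is an obvious candidate. But the covariates are unlisted, they are described as confounders rather than prognostic factors, and the run is not named as the main result. It could supply the adjustment without promising it.

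**The size is unknown, and BCVA is secondary.** Both are true. BCVA has no hypothesis in section 2.2 and no power statement. The secondary outcomes that section 6.1 calls important are IOP and clinical resolution or improvement. No sample size or error rate is affected.

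A reader might also infer stronger claims, which the documents do not support:

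- *Baseline vision is ignored altogether, with only post-baseline BCVA as the response.* This conflicts with the change outcome in section 3.5 and with the account of the interaction term for thickness in section 6.2. Baseline is probably subtracted, or is the reference visit of the response.
- *The nearly unrestricted entry range proves a large loss.* A wide baseline range tends to raise rho, which shrinks the gain when SDs are equal. Only a ceiling effect pushes the other way.
- *The contrast is biased.* Under randomisation it is not. Imbalance affects the single result obtained, not the average over repeated trials.

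**Conclusion.** The point holds as a specification gap with a small to moderate cost. On the likeliest reading, the BCVA contrast is a raw difference in change, and a covariate collected at baseline is not committed to the main analysis. With equal SDs, the intervals are wider than they need be by an amount that adjustment would reduce by about 13% at rho 0.5, falling to 2.5% at rho 0.9. If follow-up SD is 0.8 of baseline SD, the reduction is 20% to 24%. These figures rest on assumed values of rho and k, since the documents give neither. The direction does not depend on them: apart from the few degrees of freedom spent, adjustment cannot increase the variance. The conclusion also assumes that saturated is meant literally. If a common baseline mean was intended, one clarifying sentence settles the matter.

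**What to change.** In section 6.2, state that the main BCVA analysis models change at weeks 4, 8, 12, 20 and 24 with these terms: treatment by visit, the stratification variable, each eye's own baseline BCVA, and baseline BCVA by visit. Keeping baseline as a response visit with one common mean for all arms would serve equally well. Name this as the reported estimate and keep the run with the stratification variable only as support.

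Apply the same rule to the NEI VFQ-25, which is also collected at baseline, using the participant's baseline score. EuroQol need not be included on this ground, because section 3.5 uses it only to measure utilities for cost-effectiveness.

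The cost is SAP wording and one degree of freedom per visit. No new data, visits or participants are needed. The choice should be fixed before outcome data are compared by arm.

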2.1. Objective

To evaluate the relative efficacy of three commonly utilized regional corticosteroids for the regional treatment of uveitic macular edema: periocular triamcinolone acetonide; intravitreal triamcinolone acetonide; intravitreal dexamethasone implant. The primary efficacy measure will be percent change in central subfield thickness as measured by OCT at 8 weeks. Participants will continue in the study for 24 weeks in order to evaluate relative effects of the 3 treatment strategies on the duration of treatment effects, requirement for additional injections, and adverse effects.

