3.4. Primary outcome

The primary outcome is the percent change in central subfield thickness from the baseline OCT measurement at the 8-week visit. The time point of 8 weeks was chosen for assessment of the primary outcome because it encompasses the window for maximum benefit for all three treatment strategies. The results will be transformed to represent relative change. Assessment of OCT outcomes will be performed by masked readers.

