Power calculations for the primary hypotheses are based upon pair-wise comparisons of the three treatment arms: intravitreal injection of triamcinolone, dexamethasone pellet, and periocular injection of triamcinolone. A Bonferroni correction will be used to adjust for multiple comparisons, i.e. a two-sided type I error rate of $0.05/3 = 0.01667$ will be used to determine statistical significance. The sample sizes needed to provide 90% power for the superiority hypotheses (intravitreal injection or dexamethasone pellet versus periocular injection) and 80% power for the non-inferiority hypothesis (intravitreal injection versus dexamethasone pellet) were computed separately for each comparison and then the maximum sample size was selected. The primary outcome is the change in retinal thickness at the central subfield at 8 weeks. Given the skewness in the distribution of retinal thickness, a log-transformation will be used to analyze the primary outcome^{74, 87}; hence, the comparisons will be represented on a relative scale (i.e. percent of baseline) and transformed to obtain the percent change from baseline. A 20% change in retinal thickness is associated with clinically meaningful changes in visual acuity.⁷⁴ In the MUST Trial, approximately 25% of individuals had bilateral macular edema and the correlation between-eyes was 0.40 for log retinal thickness.^{4, 6} The standard deviation for change in log retinal thickness was approximately 0.33 in the MUST Trial; a conservative estimate since the treatment of macular edema was not standardized and the timing of the assessment, at 6 months after randomization, was not linked to the implementation of treatment for macular edema. Based upon the 6-month OCT evaluation in the MUST Trial, we allowed for a 10% loss to follow-up.

For the first two superiority hypotheses, we evaluated the power to show that each of the treatment methods for intravitreal corticosteroids (triamcinolone injections and dexamethasone pellets) is superior to periocular triamcinolone injections at 8 weeks. In previous studies, treatment with the dexamethasone pellet has resulted in a decrease in retinal thickness of 30%-

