The best protection against bias caused by missing data is to prevent it. We will work with coordinators and participants, as we have done in previous trials, to ensure that missing data are infrequent. Regardless, we will perform a variety of sensitivity analyses to determine the potential for bias due missing data. For a crude estimate of the range of potential impact, 'best' and 'worst' case single imputation techniques will be implement. In addition, more sophisticated approaches (e.g. multiple imputation and pattern mixture) will also be used to assess the impact of missing data^{95, 96}. For the principal sensitivity analysis, we will retain all features of the primary analysis other than how missing values for visits beyond the last one with a measured value are handled. As is implicit in the primary analysis where missing data indicators are used (e.g. "." in SAS, "NA" in R), we will treat all missing values as Missing at Random (MAR). We will impute other missing values to generate 10 pseudo-complete records for each such individual by sampling from a joint predictive distribution for the missing data given the observed data. We will use a covariance matrix equal to the estimated covariance matrix from the primary analysis, but will "take control" of the prediction mean. Varying the mean of the predictive distribution allows us to assess the sensitivity of our results to a variety of missing data scenarios. The pattern mixture model approach stratifies participants on their pattern of missing data, estimates stratum-specific parameters and then combines estimates over strata using inverse variance weights. The approach is similar to stratified analysis to adjust for potential confounders and allows for comparison of stratum-specific estimates. We stratify by three patterns: complete data, at least one internal measurement missing, and closeout weight missing (along with any other missingness).

7. Regulatory and ethical issues

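### The principal missing-data sensitivity analysis leaves a missed week-8 OCT at MAR whenever a later OCT exists, so it can overstate the robustness of the primary result

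*Combined protocol and SAP*

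**What the plan says.** Section 3.4 sets the endpoint: "The primary outcome is the percent change in central subfield thickness from the baseline OCT measurement at the 8-week visit". Under section 2.1, "Participants will continue in the study for 24 weeks", and the schedule in 3.8 has OCT at baseline and weeks 4, 8, 12, 20 and 24. Week 8 is thus the second of five post-baseline OCTs, and a missed week-8 OCT can be an internal gap.

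Section 6.2 plans several missing-data analyses:

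- **Principal sensitivity analysis.** It keeps every feature of the primary analysis "other than how missing values for visits beyond the last one with a measured value are handled". The plan adds that "we will treat all missing values as Missing at Random (MAR", and then: "We will impute other missing values to generate 10 pseudo-complete records for each such individual". The covariance comes from the primary analysis and the prediction mean is controlled: "Varying the mean of the predictive distribution allows us to assess the sensitivity of our results to a variety of missing data scenarios". No shift range or tipping-point report is specified.
- **Best-case and worst-case single imputation.** It is not limited by type of gap and is described as a crude estimate of the range of impact.
- **Pattern mixture.** There are three strata: complete data, any internal gap, and a missing closeout value. Stratum estimates are combined with inverse-variance weights.

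On the amount of missing data, section 6.1 says only that "we allowed for a 10% loss to follow-up".

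**The concern.** The scope rule suits an endpoint at the last visit. There, a missing endpoint is always beyond the last measured visit and so is always shifted. With an endpoint at week 8 of 24, missing values fall into three groups:

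1. Week 8 missing and no later OCT: shifted, and it moves the week-8 contrast.
2. Week 8 missing with a later OCT: not shifted at any setting.
3. Week 8 observed, with dropout afterwards: the later visits are shifted, but they barely move the week-8 contrast because the mean model has separate visit-by-treatment terms.

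The analysis labelled principal therefore stresses group 3, which hardly matters for the primary question, and leaves group 2 untouched. It could report that the superiority and non-inferiority conclusions withstand large departures from MAR when part of the missing primary data was never varied. This matters most for non-inferiority, the hypothesis with the least planned power (80%).

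**Working it through.** **Inputs.** From 6.1: SD of log change 0.33; 89 independent eyes per arm; margin 0.15; one-sided alpha 0.01667 for non-inferiority; two-sided 0.01667 for superiority; planned reductions of 40% and 25%; 10% loss to follow-up. Assumed, because the documents do not give them: m, the fraction of one arm with week 8 missing; q, the share of those eyes with a later OCT; the size of the shift; and the between-visit correlation.

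**The plan's own figures.**
- SE = 0.33 × √(2/89) = 0.0495.
- Non-inferiority power at a true difference of 0: Φ(0.15/0.0495 − 2.128) = 81.7% (stated 80%).
- Superiority power at log(0.75) − log(0.60) = 0.2231: 98.3% (stated 98%).
- Enrolment: 89/0.9 = 99; 99 × 1.4/(2×0.25 + 1.4×0.75) = 99 × 0.903 = 89.4 (stated 89).

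These reproduce closely enough, and no design figure is in dispute.

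**Slack for non-inferiority.** At an observed difference of 0, the half-width is 2.128 × 0.0495 = 0.1053. Slack to the margin is 0.15 − 0.1053 = 0.0447. This ignores the extra variance from imputation.

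**Tipping shift.** Let δ be the departure from the MAR prediction, applied to the dexamethasone arm. If every missing week-8 value is shifted, the contrast moves by m·δ and tips at δ = 0.0447/m. Under the rule as scoped it moves by m(1−q)·δ and tips at 0.0447/[m(1−q)]. The ratio is 1/(1−q), whatever m is. With m = 10% assumed:

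| q | Reported tipping shift (log) | Inflation |
|---|---|---|
| 0 | 0.447 | 1.00 |
| 20% | 0.559 | 1.25 |
| 50% | 0.895 | 2.00 |

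**Absolute size of what is left untested.** Take internal week-8 gaps in 2.5%, 5% or 10% of one arm, and a shift of 0.2231 beyond the MAR prediction (the planned superiority difference).

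| Internal gaps | Bias (log) | Share of margin | Non-inferiority power | Superiority power |
|---|---|---|---|---|
| none | 0 | 0 | 81.7% | 98.3% |
| 2.5% | 0.006 | 4% | 78.6% | 97.7% |
| 5% | 0.011 | 7% | 75.1% | 97.1% |
| 10% | 0.022 | 15% | 67.5% | 95.2% |

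**How much MAR already recovers.** The primary model predicts a missing week 8 from the same eye's other OCTs. If weeks 4 and 12 depart from the arm mean by the same amount as week 8, the fraction recovered is 2ρ/(1+ρ) under exchangeable correlation and 2ρ/(1+ρ²) under AR(1) per 4 weeks:
- ρ = 0.3: 46% to 55%
- ρ = 0.5: 67% to 80%
- ρ = 0.7: 82% to 94%

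Take an eye with no improvement instead of the planned 40%, a departure of log(1/0.6) = 0.511 from the arm mean. If all missing values in 10% of the arm were internal gaps, the full effect is 0.10 × 0.511 = 0.051. The unrecovered part is 0.051 × (1 − 0.94) to 0.051 × (1 − 0.46), or about 0.003 to 0.028, which is below the slack of 0.0447.

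**The case against.** **Other analyses cover the gap.** A reader might infer that these values stay MAR in everything the plan proposes. The documents do not support that: best/worst-case imputation has no restriction by gap type and moves them off MAR. This part of the objection stands. It does not make the principal analysis adequate, since the plan itself treats the best/worst bounds as crude. Pattern mixture helps less. Any internal gap enters the same stratum, an eye that also misses closeout goes to the third, and no week-8 mean is varied within a stratum.

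**The harm is not shown.** A reader might also infer that robustness is overstated as a matter of fact. One route is to set missing dexamethasone eyes at no improvement and conclude that non-inferiority falsely survives once q exceeds 12.5% (1 − 0.0447/0.0511). That treats an unseen eye under MAR as sitting at the arm mean. The model instead conditions on the eye's own visits, and under the dexamethasone schedule the week-4 and week-12 OCTs both precede the earliest permitted second injection. The threshold does not stand. Nor does an unconditional claim of anti-conservative error: the direction depends on whether unseen dexamethasone eyes did worse than MAR predicts, relative to unseen intravitreal triamcinolone eyes.

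**The 10% is loss to follow-up.** It rests on a 6-month evaluation and most naturally describes terminal missingness, which the principal analysis does shift if it occurs before week 8. It is used above only as an assumed upper value.

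**The scope is inferred.** Taken literally, MAR for 'all' missing values conflicts with imputing 'other' values under a controlled mean. The scope sentence makes the restricted reading the best supported one, and the ambiguity is itself a reason to amend.

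**Conclusion.** The point holds in a limited form. On the best-supported reading of 6.2, the principal sensitivity analysis never tests departure from MAR for a missed week-8 OCT followed by a later OCT. It can therefore overstate robustness, and for non-inferiority it does so if unseen dexamethasone eyes did worse than MAR predicts.

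The relative size is 1/(1−q) on the tipping shift, provided the shift is defined as departure from the MAR prediction. The absolute size depends on q and on how well other visits predict week 8, neither of which the documents give. It is nil with no internal gaps and small if they are few or the prediction is good. No primary decision rule, type I error rate or design figure is affected.

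**What to change.** In section 6.2:

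- Resolve the 'all'/'other' wording by stating which missing values stay MAR and which are imputed under the controlled mean.
- Apply the controlled prediction mean to every missing week-8 value, whether or not a later visit was measured, as well as to visits after the last measured one. Define the shift as departure from the MAR prediction given that eye's observed visits.
- Vary the shift separately by arm over a stated range, and report the shift at which each of the three primary conclusions changes.

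The cost is a short amendment and slightly more analysis work with the same imputation approach. The reported robustness range may look less favourable. Sample size, margin and alpha stay as they are.
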